### 13.4.2 Exploratory Endpoints

All analyses listed below are for exploratory aims. No formal comparison will be made among the cohorts. All analyses will be purely descriptive. Detailed statistical analysis plan will be developed before any analyses.

- **Visual Field Analysis:** Standard reporting from visual field tests will be collected for analysis per Study calendar ([Section 5.0](#)) and Data submission requirements ([Section 6.0](#)). Key visual field parameters will be summarized at each evaluation time point. The changes in these key visual field parameters at different time points will be explored.
- **Pituitary Hormone Replacement Therapy:** Descriptive analyses will be used assess changes in pituitary hormone replacement over time in patients with papillary craniopharyngiomas who have received BRAF/MEK inhibitors
- **Time to Response:** Time to response will be estimated using the Kaplan-Meier method within each cohort. Median overall survivals and survival rates will be estimated with their 95% confidence intervals. No formal comparison will be made among the cohorts.
- **Toxicity Associated with Radiation:** As per NCI CTCAE v 4.0, the term toxicity is defined as adverse events that are classified as possibly, probably, or definitely related to study treatment. Toxicities will be evaluated via the ordinal CTCAE standard toxicity grading. Overall toxicity associated with radiation incidence as well as radiation toxicity profiles by patient and treatment cohort will be explored and summarized. Frequency distributions, graphical techniques and other descriptive measures will form the basis of the analysis. No formal comparison will be made among the cohorts.

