#### 7.1.1 Cohort A

For Cohort A, patients should receive treatment for up to 4 cycles with vemurafenib + cobimetinib (unless progression, unacceptable toxicity, or patient withdrawal from study occurs). See [Section 12.0](#) for additional information. After 4 cycles of vemurafenib and cobimetinib, surgery or radiation for definitive therapy should be performed. Continuation of vemurafenib and cobimetinib beyond 4 cycles in cohort A will require approval from the radiation oncology chair and study chair. If patient stays on study for longer than 4 cycles, visits and labs at the beginning of every cycle are still required with scans every 2 cycles, as per the study calendar.

- **For patients that achieve CR**, they will undergo definitive radiation.
- **For patients with any response that is not CR or better**, the decision of therapy between surgery, or radiation, or both, is at the discretion of the treating physician.

**For patients who go on to receive radiation**, the pre-treatment scan would be used as a guide for radiation planning. See [Section 7.2](#) for radiation guidelines. Vemurafenib and cobimetinib need to be stopped at least two weeks prior to initiation of radiation therapy. For purposes of radiation planning, if duration of BRAF/MEK inhibitor treatment needs to be extended this will be allowed, for a maximum length of 4 additional weeks (i.e., 5 cycles maximum).

**In special cases**, if radiation or surgery are not recommended for the patient because of potential risks, then the patient may continue on cobimetinib and vemurafenib past 4 cycles, until disease progression or unacceptable adverse events. **However, continuation of treatment can only be granted with approval from the radiation oncologist and study chair.** A request, with accompanying rationale, must be sent to the radiation oncologist and protocol coordinator. Approval must be obtained via email prior to Cycle 5 drug shipment. The email containing the approval must also be submitted via Rave as supporting documentation.

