## 12.0 END OF TREATMENT/INTERVENTION

### 12.1 Duration of treatment

**12.1.1 CR, PR, or SD:** Patients who are in CR, PR or SD will continue on therapy as outlined below:

- Cohort A: Patients can continue on therapy for a total of 4 cycles in cohort A, and then go on to receive radiation, surgery or both as outlined in [Section 7.1.1](#). In special circumstances, continuation of therapy with vemurafenib and cobimetinib may be granted, but only with approval from the radiation oncology chair (see [Section 7.1.1](#) for additional details). If continuation is approved, then therapy with cobimetinib and vemurafenib can continue until documented progression, unacceptable adverse events, or drug hold >28 days.
- Cohort B: Patients can continue therapy with cobimetinib and vemurafenib until documented progression, unacceptable adverse events, or drug hold >28 days (see [Section 7.1.2](#)). After treatment is completed or discontinued, patients will be followed per the study calendar in [Section 5.0](#).

**12.1.2 Disease progression:** Remove from protocol therapy any patient with disease progression. Document details, including tumor measurements, on data forms.

After disease progression, patients should be followed for survival per the study calendar ([Section 5.0](#)).

**12.1.3 Discontinuation of study agent:** If the patient discontinues protocol therapy due to reasons other than PD (i.e. for unacceptable adverse events, drug hold >28 days), prior to the completion of planned therapy as per [Section 7.0](#), patients should go on to clinical and survival follow up per the study calendar ([Section 5.0](#)). This includes:

- Patients who discontinue treatment before the end of 4 cycles of treatment to begin alternative therapy.
- Patients who discontinue continued treatment with vemurafenib and cobimetinib to begin alternative therapy (i.e. patients on Cohorts A or B who choose to continue therapy with vemurafenib and cobimetinib post the initial 4 cycles).

**12.1.4 Discontinuation of study agent in patients with expected AEs:** See [Section 8.2.4](#) for more information.

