- **Duration of Response:** Duration of response is defined from the time measurement criteria are met for CR or PR (whichever is first recorded) until the first date that progressive disease or death is documented. Only patients who have achieved a CR or PR will be included in this analysis. Patients who fail to return for evaluation or patients who are still alive and have not progressed at the time of analysis will be censored for progression at the time of the last tumor assessment. Duration of response will be estimated using the Kaplan-Meier method within each cohort. Median overall survivals and survival rates will be estimated with their 95% confidence intervals. No formal comparison will be made among the cohorts.

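### Time to response is planned by Kaplan-Meier with no stated population or rule for patients who can no longer respond on drug; if they are censored, the curve can overstate response

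*Combined protocol and SAP*

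**What the plan says.** For time to response, Section 13.4.2 gives one sentence of method: "Time to response will be estimated using the Kaplan-Meier method within each cohort". It adds a summary by median and survival rates, and no formal comparison of cohorts. It gives no time origin, population or censoring rule. The same section says of all exploratory endpoints that "All analyses will be purely descriptive" and that "Detailed statistical analysis plan will be developed before any analyses".

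The duration-of-response bullet in Section 13.4.1 is fuller. It defines the start and end of the interval, restricts the population ("Only patients who have achieved a CR or PR will be included in this analysis") and states that patients without the event, or who do not return, "will be censored for progression at the time of the last tumor assessment". Its summary sentence reads "Median overall survivals and survival rates will be estimated with their 95% confidence intervals". The same sentence closes the time-to-response bullet, although overall survival is the endpoint of neither.

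Other sections list the ways in which a patient leaves drug treatment:

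- **Progression.** Section 12.1.2: "Remove from protocol therapy any patient with disease progression".
- **Toxicity or a long hold.** The Schema and Section 12.1 end treatment for an unacceptable adverse event or a drug hold of more than 28 days.
- **Definitive therapy, Cohort A.** Section 7.1.1: "After 4 cycles of vemurafenib and cobimetinib, surgery or radiation for definitive therapy should be performed". Continuation beyond that point needs approval.
- **Other therapy, Cohort B.** Section 7.1.2 leaves the choice after 4 cycles to the treating physician: radiation, surgery or more drug.

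**The concern.** Section 13.2.1 counts a response only if it is achieved during treatment with the two inhibitors. A non-responder who leaves the drugs has therefore lost the chance of the event. That is a competing event, not ordinary loss to follow-up.

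Kaplan-Meier has no place for a competing event. If such a patient is censored on leaving, which is a common default, the method assumes that he or she would have gone on to respond at the same rate as patients still on drug. Each later response then counts for more than one patient's share, and the curve rises above the proportion who responded.

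At stake is a published curve, plateau and possibly a median that do not match the response rate reported for the same 16 patients. In a small single-arm trial, readers are likely to set these side by side.

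**Working it through.** **Inputs.** Each cohort has n = 16 evaluable patients (Section 13.2.2). Imaging is every 2 cycles of 28 days (Sections 7.1 and 13.2.1), so on-drug scans fall at weeks 8 and 16 during the first 4 cycles. The documents give no expected number of early stops without response and no response pattern over time, so both are assumed below and shown as ranges.

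**The plan's own figures.** None is given for time to response. The primary design reproduces: an exact two-stage binomial with 9 then 16 patients, continuing on at least 1 response and succeeding on at least 3, gives one-sided alpha 0.0406 (stated 0.041) and power 0.8864 at a 30% rate (stated 0.886). Neither uses the time-to-response curve.

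**Formulas.** Let r1 patients respond at week 8 and r2 at week 16, and let d non-responders leave between the scans and be censored.

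- Kaplan-Meier: 1-KM = 1 − (1 − r1/n) × (1 − r2/(n − r1 − d)).
- Cumulative incidence with leaving as a competing event, and no other censoring: (r1 + r2)/n.

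With d = 0 the product is (n − r1 − r2)/n and the two agree. Any d > 0 shrinks the second denominator, so 1-KM can only be equal or higher.

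**Case 1: 6 + 4 responses in 16.** Cumulative incidence is 10/16 = 62.5%.

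| d | 1-KM at week 16 | Excess (points) |
|---|---|---|
| 0 | 1 − 0.625 × 6/10 = 62.5% | 0 |
| 1 | 1 − 0.625 × 5/9 = 65.3% | 2.8 |
| 2 | 1 − 0.625 × 4/8 = 68.8% | 6.3 |
| 3 | 1 − 0.625 × 3/7 = 73.2% | 10.7 |
| 4 | 1 − 0.625 × 2/6 = 79.2% | 16.7 |

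Both curves stand at 37.5% at week 8 and pass 50% at week 16, so the median is week 16 throughout.

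**Case 2: 4 + 3 responses, d = 4.** 1-KM = 1 − 0.75 × 5/8 = 53.1%, against 7/16 = 43.8%. Kaplan-Meier reports a median at week 16; on the cumulative incidence the median is not reached.

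**Wider range.** Now spread 0 to 6 early stops over the time before week 8 and between the scans. With 5 responders, 1-KM runs from 31.2% to 45.1% against 31.2%. With 7 responders it runs from 43.8% to 65.4% against 43.8%.

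**Which exits matter.**

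- *Cohort A, definitive therapy after cycle 4.* With 3 + 2 responses, no earlier stop and everyone leaving after the week-16 scan, 1-KM = 1 − (13/16)(11/13) = 31.2% = 5/16. There is no bias up to week 16.
- *Cohort A with approved continuation.* Take the same start, 9 patients leaving for surgery or radiation and 2 continuing, of whom 1 responds at week 24. 1-KM = 1 − (11/16)(1/2) = 65.6%, against 6/16 = 37.5%.
- *Cohort B after cycle 4.* Suppose 1 stop before week 8 and then 3 responses; 1 stop and then 2 responses at week 16; then 5 leave and 1 of the remaining 4 responds at week 24. 1-KM = 1 − (12/15)(9/11)(3/4) = 50.9%, against 6/16 = 37.5%.

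In the two week-24 examples the comparison is with the crude proportion responding by week 24. For Cohort B that is not the primary response rate, which stops at cycle 4.

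**The case against.** The bias depends on two things that the plan does not state. The words about estimation within each cohort do not settle the population: the same words are used for duration of response, which is limited to responders. In a responders-only analysis no non-responder is in the risk set and the bias cannot arise. Nor does the plan say that patients are censored when they stop the drugs. If non-responders stay at risk to the end of follow-up, 1-KM equals the cumulative incidence. This stands, and it makes the point conditional. It does not remove it: the neighbouring bullet states its population and censoring rule, this one states neither, and a responders-only analysis in which everyone has the event would not need Kaplan-Meier.

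The analysis is exploratory and descriptive, and a detailed plan is still to be written. That also stands, and it limits the importance. But the method is already named, and a later plan could carry it forward unchanged.

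A reader might go further and infer that the median will be shortened, or that definitive surgery or radiation in Cohort A drives the problem. The documents support neither. With scans 8 weeks apart the median can only fall on a scan time and often stays where it is, as in case 1. Cohort A's planned definitive therapy follows cycle 4 and adds no bias up to week 16.

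**Conclusion.** The point holds as a conditional one of minor importance. Section 13.4.2 names a method that is unsuited to an endpoint with competing events and leaves open the choices that decide whether it misleads. If all patients are included and non-responders are censored on leaving drug, 1-KM is at or above the true incidence of response. In the 6 + 4 pattern the excess is 0 to 16.7 points for an assumed 0 to 4 leavers.

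The early-stop counts are assumptions. The nearest figure in the documents is Table 1 in Section 1.6.1, where 24 of 336 melanoma patients on vemurafenib alone (7%) stopped for adverse events. That is about 1 in 16 (0.07 × 16 = 1.1) and corresponds to an excess of 2.8 points in that pattern if the one patient is a non-responder leaving between the scans. Progression and withdrawal would add to it, and the combination may differ.

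Early progression and toxicity stops are the main source. Surgery or radiation matters mainly in Cohort B after cycle 4 and when some Cohort A patients are approved to continue. The primary response rate, its decision rules, alpha and power are unaffected. The overall-survival wording in the two bullets is clerical.

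**What to change.** In the time-to-response bullet of Section 13.4.2, replace Kaplan-Meier with the cumulative incidence of response from first dose (Aalen-Johansen) in all evaluable patients of each cohort. Treat progression, death, permanent stop of both drugs, and start of surgery or radiation as competing events. Beside it, report the median and range of time to response among responders.

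As an editorial correction, change the summary sentence under both duration of response (Section 13.4.1) and time to response (Section 13.4.2) so that it names the median of that endpoint.

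The cost is a few lines of wording and standard software, with no change to sample size or primary analysis. If patients stop early without responding, the reported curve will be lower than the censored Kaplan-Meier curve and will agree with the proportion who responded.

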## 13.5 Monitoring the study

### 13.5.1 Adverse event stopping rule

The stopping rule specified below is based on the current knowledge available. We note that the Adverse Event Stopping Rule may be adjusted in the event of either (1) the study re-opening to accrual or (2) at any time during the conduct of the trial and in consideration of newly acquired information regarding the adverse event profile of the treatment(s) under

investigation. The study team may choose to suspend accrual because of unexpected adverse event profiles that have not crossed the specified rule below.

The AE stopping boundaries are defined as follows: at any time, if we observe events considered at least possibly related to study treatment (i.e., an adverse event with attribute specified as “possible”, “probable”, or “definite”) within each cohort that satisfy the following criteria:

- if 2 or more patients in the first 10 treated patients (or 20% of all patients after 10 are accrued) experience a grade 4 or higher adverse event that excludes the following:
  - Hematologic Events
  - Any Asymptomatic Metabolic/Laboratory Abnormalities (excluding high CPK)

In the event that the boundary for the Adverse Event Stopping rule is crossed, the study team will consult with CTEP to evaluate the safety risk for participants of the trial and determine if a temporary suspension of accrual is needed.

We note that we will review grade 4 and 5 adverse events deemed “unrelated” or “unlikely to be related”, to verify their attribution and to monitor the emergence of a previously unrecognized treatment-related adverse event.

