### 13.3 Sample size, accrual time and study duration

#### 13.3.1 Sample size

The study design to be utilized is fully described in [Section 13.1](#). There will be 16 evaluable patients assigned to each cohort (total of 32 evaluable patients). We anticipate accruing an additional 2 patients in each cohort to account for ineligible patients or cancellations. Thus the maximum target accrual is 36 in total. In the event that the additional accrual does not produce the required number of evaluable patients, we retain the option of continuing accrual until that goal is met.

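### The adverse event boundary in 13.5.1 does not say whether its 20% is of treated or accrued patients, and as worded it leaves fatal hematologic events uncounted

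*Combined protocol and SAP*

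**What the plan says.** Section 13.5.1 of the combined protocol and SAP defines the boundary separately for each cohort. It counts adverse events judged possibly, probably or definitely related to treatment. The number of patients that crosses it is given as "if 2 or more patients in the first 10 treated patients (or 20% of all patients after 10 are accrued"). What each of those patients must have had is put this way: "experience a grade 4 or higher adverse event that excludes the following". Two exclusions follow. One is "Hematologic Events", with no grade attached. The other is asymptomatic metabolic or laboratory abnormalities, from which high CPK is carved out.

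On crossing, "the study team will consult with CTEP to evaluate the safety risk for participants of the trial" and decide whether accrual should be paused. Below the boundary, "The study team may choose to suspend accrual because of unexpected adverse event profiles that have not crossed the specified rule below".

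Section 13.3.1 gives the cohort size: "There will be 16 evaluable patients assigned to each cohort". It then adds a margin: "We anticipate accruing an additional 2 patients in each cohort to account for ineligible patients or cancellations". Section 12.2 sets follow-up for patients who are registered but never treated, so the plan itself foresees that accrued can exceed treated.

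**The concern.** The numerator can come only from patients who took study drug. The first clause uses a matching denominator, treated patients. The second speaks of all patients and mentions only accrual. If cancelled or not yet dosed patients enter that denominator, the observed proportion is diluted just as a cohort is filling up, and two people applying the rule to the same data could disagree on whether it has been crossed. Section 13.5.3 shows that the protocol can be explicit: its imaging rule specifies patients who have had at least one dose.

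The second matter is independent of the first. The rule covers grade 4 and above, so it is meant to include deaths. The hematologic exclusion then removes every grade of that class, including a death attributed to treatment.

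**Working it through.** **Inputs.** Boundary of 2 in the first 10 treated, then 20% (13.5.1). 16 evaluable patients plus 2 extra per cohort (13.3.1). The plan gives no operating characteristics for this rule, so there is no stated figure to reproduce. Two consistency checks pass: 2/10 = 20%, so the clauses agree at 10 patients; and 2 × (16 + 2) = 36, the stated maximum accrual.

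**Thresholds.** Read 20% as at least 20%. The number of patients with events needed at denominator n is 0.20 × n rounded up: 2 at n = 10, 3 at n = 11 to 15, 4 at n = 16 to 18.

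**Where the two readings differ.** Let T be treated, A accrued and k patients with events. The accrued reading is silent where the treated reading is not when k ≥ 0.2T but k < 0.2A. With T above 10 and A − T at most 2, there are three such states, all with k = 3:

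| Treated | Accrued | k/T | k/A |
|---|---|---|---|
| 14 | 16 | 21.4% | 18.8% |
| 15 | 16 | 20.0% | 18.8% |
| 15 | 17 | 20.0% | 17.6% |

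Each also requires at most 1 event in the first 10 treated; otherwise the first clause has already been met. At the planned end, 16 treated and 18 accrued, both readings need 4 (0.2 × 16 = 3.2 and 0.2 × 18 = 3.6, each rounded up).

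**Chance of ever crossing over 16 treated patients.** Check after each patient: crossing means k ≥ 2 up to T = 10, then k ≥ 0.2 × (T + d), where d is the number untreated, held constant. At a true rate p = 0.20:

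- First 10: P(0 events) = 0.8^10 = 0.1074 and P(1 event) = 10 × 0.2 × 0.8^9 = 0.2684. The first clause alone crosses with probability 1 − 0.3758 = 62.4%.
- d = 0: not crossing requires a total of at most 2 through T = 15. The probability is 0.1074 × 0.9421 + 0.2684 × 0.7373 = 0.2991, so crossing is 70.1%.
- d = 2: not crossing requires at most 2 through T = 13 and at most 3 through T = 16. The probability is 0.1074 × 0.9789 + 0.2684 × 0.8520 = 0.3338, so crossing is 66.6%.

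The documents give no expected event rate for this rule, so a range was scanned:

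| True rate | d = 0 | d = 1 | d = 2 | Loss, d = 2 (points) |
|---|---|---|---|---|
| 5% | 9.4% | 9.1% | 8.9% | 0.5 |
| 10% | 29.8% | 28.7% | 27.8% | 2.0 |
| 15% | 51.8% | 49.9% | 48.6% | 3.2 |
| 20% | 70.1% | 68.1% | 66.6% | 3.5 |
| 30% | 91.2% | 90.0% | 89.2% | 2.1 |
| 40% | 98.2% | 97.8% | 97.6% | 0.7 |

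**If the first clause lapses.** The text does not say whether it continues once 10 are accrued. If it does not, 2 of 10 treated is also silent with 11 accrued (2/11 = 18.2%) or 12 accrued (2/12 = 16.7%).

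**Hematologic exclusion.** No arithmetic is needed. Section 13.5.1 excludes the class without a grade. Section 9.4.2, dealing with expedited reporting, exempts hematosuppression only at grades 3 and 4. The closing paragraph of 13.5.1 promises a review of grade 4 and 5 events, but only those judged unrelated or unlikely to be related, so it does not reach a related event that the exclusion has removed.

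**The case against.** The strongest reply on the denominator is that 'accrued' only fixes when the second clause begins, and that 'all patients', coming straight after 'treated patients', means all treated patients. That reading is tenable, and on it there is no gap. A reader might infer that the rule plainly switches to accrued patients and is therefore looser than 20%. The text does not say so; it is silent on the point.

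Even on the accrued reading the effect is small. A reader might note that 16 of 18 understates the rate by 11% in relative terms (1 − 16/18), but at 16 treated and 18 accrued the threshold is 4 either way. Two untreated throughout uses the plan's whole margin, and that margin also covers ineligible patients, who may stay on treatment under Section 12.2. Delay between registration and first dose is at most 10 days (Section 7.0) and corrects itself. Against this, 13.3.1 keeps the option of further accrual, so 2 is the planned margin, not a hard cap.

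On the hematologic exclusion, all deaths on study need routine and expedited reporting whatever the cause (Section 9.4), adverse event summaries are reviewed monthly (13.6.1), and the team may suspend accrual without a crossing. One death alone would not reach the boundary of 2. Section 1.6.3 reports no grade 5 events in BRIM-7, and describes none of the six patients with grade 5 events on the combination in CoBRIM as having a hematologic one. All of this stands and limits the harm. It does not make the boundary count the event.

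**Conclusion.** Two separate and minor wording defects stand.

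1. The denominator after 10 patients is undefined. If it means treated, nothing is lost. If it means accrued, the threshold beyond 10 treated is one patient too high in three states, and the loss in crossing probability is at most about 3.5 points over the true rates scanned (5% to 40%), largest at 20%. This assumes 2 untreated patients throughout, the first clause still in force, and 20% read as at least 20%.
2. As worded, a treatment-related grade 5 hematologic event does not count toward the boundary. The documents give no frequency for such an event, so its impact cannot be sized beyond one uncounted patient per occurrence. The grade 3/4 limit in 9.4.2 suggests an oversight.

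A reader might join the two and conclude that the hematologic exclusion also keeps the rule silent on qualifying events. It does not: excluded events do not qualify by definition. Nor does the asymptomatic-laboratory exclusion hide deaths, because a fatal event is not asymptomatic. And because a crossing leads to consultation, neither defect means that an automatic stop would be missed.

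**What to change.** In 13.5.1, use treated patients in both clauses, for example by wording the second as 20% of all treated patients once more than 10 have been treated, and state whether the first clause stays in force after that point. Limit the hematologic exclusion to grade 4, so that grade 5 events at least possibly related to treatment count, in line with the limit in 9.4.2. The asymptomatic-laboratory exclusion needs no change.

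The cost is a few words and a slightly higher chance of a consultation with CTEP. The sample size, the efficacy design and patients' treatment are unaffected.
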